### 6.5.3 Missing Outcome and Covariates

Participants are included in the analyses to the extent of their available data; missing immunogenicity data are not imputed. See Sections 5.5 and 5.7 and definition of anti-CHIKV human SNA assay titer in Section 6.3.

Participants with missing categorical data are counted in missing or unknown categories when appropriate. Participants with missing numeric data are treated as missing completely at random when calculating summary statistics. For likelihood-based analyses (e.g., regression), missing at random is assumed.

As sensitivity analyses for the coprimary endpoints (difference in anti-CHIKV SNA seroresponse rate between PXVX0317 and placebo at Day 22 and GMTs at Day 22), missing immunogenicity outcome data at Day 22 are imputed conservatively as described below. Participants who have an out-of-window result at Day 22 (before Day 19 or after Day 27), are seropositive at baseline, or have an exclusionary PD are included in the mITT population but not the IEP population for these sensitivity analyses.

- Nonresponder analysis. Participants' missing Day 22 anti-CHIKV SNA titer value is imputed as the assay LLOQ/2, even for participants in the PXVX0317-vaccinated group.
- Last observation carried forward (LOCF) analysis. Participants' Day 15 immunogenicity value is substituted for the missing Day 22 anti-CHIKV SNA titer value.

The endpoints are recalculated using each method of conservative imputation and reported for the mITT population to assess the robustness of primary endpoint results to informative missingness.

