Study procedures/assessments will occur at: Screening (Visit 1), to occur no more than 30 days prior to Day 1 of IP administration; Day 1 (Visit 2, Baseline, Randomization, and IP Administration); Day 15 (Visit 3); Day 22 (Visit 4); Day 29 (Visit 5, telephone contact); Day 92 (Visit 6, telephone contact); Day 183 (Visit 7, End of Study) or Early Discontinuation Visit (EDV). The per-participant estimated total study duration is 212 days (includes the 30-day screening window).

Solicited AEs (collected from Day 1 through Day 8) will consist of local adverse reactions (injection site pain, redness, and swelling) and systemic adverse reactions (fever, chills, fatigue, headache, myalgia, arthralgia, and nausea). Unsolicited AEs will be collected from

Day 1 through Day 29. Serious adverse events, MAAEs, and AESI will be collected from Day 1 through Day 183 End of Study Visit.

The immune response to PXVX0317 will be measured by CHIKV SNA responses up to 182 days after dosing (Day 183). CHIKV SNA levels will be measured by a validated CHIKV luciferase-based assay (hereafter referred to as human SNA assay) developed by the sponsor (see Section 7 for human SNA assay description).

Statistical Methods:

Seroresponse rates: Proportions (percentages) of participants in PXVX0317 and placebo groups with a seroresponse at Day 15, Day 22, and Day 183 will be summarized with two-sided 95% CIs based on the Wilson score method. This analysis will be primarily based in the immunogenicity evaluable population (IEP) and repeated for the modified intent-to-treat (mITT) population as a measure of the robustness of the findings. The significance of the treatment group difference will be assessed using chi-square tests at each visit based on both age groups combined with a two-sided alpha=0.05.

The difference in CHIKV SNA seroresponse rates (PXVX0317 minus placebo) among baseline seronegative participants will be calculated along with the two-sided 95% CI for the difference based on the Newcombe hybrid score method at Day 15, Day 22, and Day 183. At Day 22, the lower bound of the two-sided 95% CI for the difference in seroresponse rates (PXVX0317 minus placebo) for both age strata combined must meet or exceed █ for clinical relevance to be demonstrated.

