### 2.2 Study Design and Conduct

This is a phase 3, randomized, double-blind, placebo-controlled, parallel-group study with two treatment groups. This multicenter study is conducted in the US with up to 10 sites. At least 400 enrolled healthy US participants  $\geq 65$  years of age and older are enrolled, stratified in two age subgroups ( $\geq 65$  to  $< 75$  and  $\geq 75$  years of age) with a target of 25% enrollment of participants  $\geq 75$  years of age. Participants are randomized in a 1:1 ratio to receive either a

single intramuscular (IM) dose of PXVX0317 or placebo at Day 1. With 400 participants enrolled, the treatment group totals are estimated as follows:

- Group 1- PXVX0317: n=200
- Group 2- Placebo: n=200

The per participant estimated total study duration is 212 days (including screening). The screening window is no greater than 30 days prior to Day 1 (randomization and administration of investigational product [IP]). Screening assessments include informed consent, review of eligibility criteria, medical history, prior and concomitant medications, demography, physical examination including height and weight for body mass index calculation, vital signs, urine toxicology screening per investigator's discretion, and viral markers for hepatitis B surface antigen (HBsAg), hepatitis C (HCV) and human immune deficiency virus 1 and 2 (HIV-1/HIV-2).

[figure not shown]
Prior to IP administration on Day 1 (baseline), eligibility, medical history and concomitant medications are reviewed, and a baseline anti-CHIKV SNA sample is drawn. Vital signs including blood pressure, heart rate, respiratory rate and temperature are taken on Day 1 before and after IP administration. Directed physical examinations are performed if indicated at Days 1, 15, 22 and Day 183 End of Study Visit (EOS). The immune response to PXVX0317 is measured by anti-CHIKV SNA at Day 15, Day 22 (coprimary endpoints are at Day 22) and Day 183 EOS (or at Early Discontinuation/ Withdrawal). No safety laboratory samples are collected as part of the study.

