### 6.1.2 Geometric Mean Titers and Geometric Mean Fold Increase

The superiority of PXVX0317 vaccine immunogenicity over that of placebo is explored further by comparing Day 22 GMTs derived from a linear model with a one-sided alpha=0.025. The primary model is an analysis of variance (ANOVA), with  $\log_{10}$ -transformed anti-CHIKV SNA titers ( $\log_{10}$ ) as the dependent variable and treatment group and study site as the fixed effects in the model. No interaction term is used. The adjusted least square means and their 95% CIs calculated based on the ANOVA are back transformed and reported as the group GMT values. No adjustment for multiplicity is applied. See Section 6.4 for statistical hypothesis, Section 6.9 for multiplicity considerations, and Section 8.4.1.2 for analysis outputs. Identical methods are used for treatment group comparison of GMTs at Days 15 and 183.

Geometric mean fold increase (GMFI) from baseline (Day 1) to Days 15, 22 and 183 is calculated using the difference from Day 1 in  $\log_{10}$ -transformed titers as the dependent variable in the ANOVA model. The adjusted least square means and their 95% CIs calculated based on the ANOVA are back transformed and reported as the group GMFI values. The median, minimum and maximum titers and fold-increases are based on the non-transformed scale.

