## 6.4 Statistical Hypotheses

### 6.4.1 Coprimary Immunogenicity Endpoints

The study is a multicenter, randomized, two-arm, active-controlled study to evaluate PXVX0317 vaccine vs. placebo. A successful trial means success on each of the coprimary endpoints: seroresponse ( $H_{A1}$ ) and GMT ( $H_{A2}$ ), both at Day 22 using the IEP. Statistical hypotheses for each of these endpoints are discussed in turn in this section. The familywise error rate is fixed at a two-sided alpha of 0.05 by the requirement that both coprimary endpoints must be met for a successful outcome.

In standard statistical notation, the null and alternative hypotheses are:

$H_0$ :  $H_{A1}$  not met or  $H_{A2}$  not met

$H_A$ :  $H_{A1}$  met and  $H_{A2}$  met

where  $H_{A1}$  and  $H_{A2}$  are the alternative hypotheses for each of the coprimary endpoints as defined below in this section.

The first coprimary endpoint is the treatment group-specific estimates and difference between treatment groups in anti-CHIKV SNA seroresponse rates using a titer of █ at Day 22 in the IEP for both age strata pooled and is tested in two ways. First, the lower bound of the Newcombe hybrid score method two-sided 95% CI on the difference in seroresponse rates between PXVX0317 and placebo must be █. Secondly, the null hypothesis of no difference between seroresponse rate percentages is tested using a two-sided chi-square test with alpha=0.05. In standard statistical notation, the null and alternative hypotheses for the first coprimary endpoint are as follows:

$H_01: (P_{PXVX0317} - P_{placebo}) \leq 0$  using a two-sided chi-square test  
 $H_{A1}: (P_{PXVX0317} - P_{placebo}) > 0$  using a two-sided chi-square test  
where  $P_{PXVX0317}$  is the percentage of PXVX0317 participants and  $P_{placebo}$  is the percentage of placebo participants with seroresponse at a titer of █ at 21 days after vaccination in the IEP for both age strata pooled.

The second coprimary endpoint tests for a significant difference in treatment group-specific Day 22 GMTs in the IEP for both age strata pooled, as derived from a one-sided alpha=0.025 ANOVA with  $\log_{10}$ -transformed anti-CHIKV SNA titers ( $\log_{10}$ ) as the dependent variable and treatment group and study site as the fixed effects. The adjusted least square means and their 95% CIs calculated based on the ANOVA are back transformed and reported as the group GMT values. In standard statistical notation, the null and alternative hypotheses are:

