## 6.6 Adjustment for Covariates

Beyond the inclusion of site in the immunogenicity ANOVA models described in Section 6.1, no further adjustment for covariates is performed. Immunogenicity analyses are conducted for both age strata pooled as well as by separate age strata.

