## 6.8 Subgroup Analyses

Summaries pool both age groups and are repeated separately for each age group. Analyses of the primary immunogenicity and safety endpoints are also summarized by sex, race, and ethnicity group along with treatment group. Summaries by baseline anti-CHIKV SNA serostatus are reported if the baseline (Day 1) seropositive rate is  $\geq 10\%$ .

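### The mITT robustness analyses count Day 1 antibody as response and show no outcome by baseline serostatus, so a gap between mITT and IEP cannot be attributed; the primary result is unaffected

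*SAP*

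**What the plan says.** - **Populations (SAP 5.3).** The mITT needs vaccination and one post-injection titer, with no condition on Day 1. The IEP also requires a Day 1 titer below the LLOQ. The mITT repeat is described as a check of robustness.
- **Sensitivity analyses (SAP 6.5.3).** Nonresponder and LOCF imputation of Day 22 are reported for the mITT, to probe informative missingness. Participants who "are seropositive at baseline, or have an exclusionary PD are included in the mITT population but not the IEP population".
- **Seroresponse (SAP 6.3, 6.1.1).** It is a titer at or above a redacted threshold, with no reference to Day 1 and no covariate adjustment.
- **GMT (SAP 6.1.2, 6.6).** The ANOVA on log10 titer has treatment and site as effects. Beyond site, "no further adjustment for covariates is performed".
- **Endpoints that use Day 1 (SAP 8.4.2.3, 8.4.2.4).** GMFI and 4-fold rise are specified for the IEP only.
- **Serostatus counts (SAP 8.2.1).** Baseline serostatus is tabulated by arm for the randomized, safety, mITT and IEP populations, unconditionally.
- **Serostatus outcomes (SAP 6.8, Appendix I).** "Summaries by baseline anti-CHIKV SNA serostatus are reported if the baseline (Day 1) seropositive rate is" at least 10%. The listed tables, 14.2.1.1.5 and 14.2.2.1.5, are titled for the IEP.

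**The concern.** A placebo recipient who already has a titer above the threshold on Day 1 will normally still have it on Day 22 and so counts as a responder. Pre-existing antibody raises the placebo rate much more than the vaccine rate, which is already high, and so shrinks the mITT difference. In the GMT comparison it raises the placebo mean and adds between-participant variance that the model leaves unexplained, although the Day 1 titer is available.

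What is at stake is how the robustness check can be read. If the mITT result is weaker than the IEP result, the reader needs to know whether missing samples, out-of-window samples, deviations or prior antibody explain it. The planned outputs give the number of seropositives in each arm but no mITT outcome with them set aside. The conditional serostatus tables do not help: on the IEP their seropositive stratum is empty by definition.

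The nonresponder analysis adds a further distortion. A seropositive participant with no Day 22 sample is set to LLOQ/2, below that participant's own measured baseline.

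**Working it through.** **1. The plan's own figures.** SAP 4.1 gives 180 evaluable per arm, 5% for placebo, half-widths of 5.4% and 6.9%, and power above 99.9%. The vaccine rates are redacted. The simple (Wald) half-width is 1.96 × √[p(1−p)/180 + 0.05 × 0.95/180].
- p = 0.90 gives 5.42%.
- p = 0.77 gives 6.92%.

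These rates are inferred from the half-widths and are used below as assumptions. The stated power holds for any vaccine rate of at least 0.231, so it does not depend on the redacted value.

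**2. Inputs for the dilution.**
- Allocation: "Participants are randomized in a 1:1 ratio", with "Group 1- PXVX0317: n=200" and the same for placebo (SAP 2.2).
- mITT size: 190 per arm, an assumption between 180 evaluable and 200 randomized.
- Seropositive fraction s: not given for this trial. The range 1% to 9% lies below the 10% trigger.
- Every seropositive is taken to be above the threshold at Day 22 in both arms. This makes the result an upper limit.

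**3. Formula.** In each arm the mITT rate is s + (1−s)p, so the mITT difference is (1−s)(p₁−p₀). One seropositive in 190 raises the placebo rate by (1−0.05)/190 = 0.50 points and the vaccine rate by (1−0.90)/190 = 0.05 points. The lower bound is Newcombe's: d − √[(p₁−l₁)² + (u₀−p₀)²], where l₁ and u₀ are Wilson limits. At s = 0 this is 0.85 − √[(0.9000−0.8491)² + (0.0909−0.0500)²] = 0.785.

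**4. Seroresponse, 90% vs 5% in seronegatives.**

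| s | Vaccine | Placebo | Difference (points) | Fall | Lower bound |
|---|---|---|---|---|---|
| 0 | 90.0% | 5.0% | 85.00 | – | 78.5% |
| 1% | 90.1% | 5.95% | 84.15 | 0.85 | 77.5% |
| 2% | 90.2% | 6.9% | 83.30 | 1.70 | 76.5% |
| 5% | 90.5% | 9.75% | 80.75 | 4.25 | 73.6% |
| 9% | 90.9% | 13.55% | 77.35 | 7.65 | 69.9% |

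With 77% vs 5% the lower bound falls from 64.3% to 62.7%, 60.2% and 57.1% at 2%, 5% and 9%. Restricting to Day 1 seronegatives restores 85.0 or 72.0 points.

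**5. GMT, by simulation.** All titer inputs are assumed, with LLOQ 15 throughout.
- Set A: 190 per arm, seropositive Day 1 log10 mean 2.7, vaccine Day 22 mean 3.1, SD 0.5. Adding log10 Day 1 titer takes the standard error of the log10 difference from 0.0409 to 0.0381 at 2%, 0.0467 to 0.0408 at 5% and 0.0529 to 0.0440 at 9%. The cuts are 6.8%, 12.6% and 16.8%.
- Set B: 200 per arm, seropositive Day 1 mean 2.3 (SD 0.4), vaccine mean 3.0, SD 0.5. The cuts are 2–4% at 2%, 3–8% at 5% and 4–13% at 10%. The lower end applies if vaccinated seropositives do not respond at all.
- Dilution in set B: the GMT ratio is about 133 in seronegatives, 121–125 at 2% and 105–115 at 5%. The covariate barely moves it (104.9 without, 105.8 with, at 5% and no response in seropositives).

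**6. Superiority.** With 200 per arm, chi-square power stays at 1.000 and the GMT estimate exceeds 28 standard errors even at 20% seropositive.

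**The case against.** The strongest reply is that nothing formal depends on the mITT. Both success criteria apply to the IEP (Protocol 9.4.1, SAP 6.9.1), which already excludes seropositives and participants without a Day 1 titer. Dilution can only make the vaccine look worse, so it cannot create a false success. This stands, and it is why the point is minor.

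The size is also uncertain. The trial is US only. The one seropositive figure in the documents, about 20%, comes from endemic Caribbean sites (Protocol 1.4.2). SAP 4.1 allows 10% non-evaluable for all reasons, and 9% from serostatus alone would use nearly all of that. At 1% to 2% the shift is under 2 points. This also stands.

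Counting anyone above the threshold is consistent with the definition of seroresponse as presumptive seroprotection, and including all comers is explicit. That is a fair reason to keep the all-comer row and not to redefine response. Requiring a 4-fold rise would replace the endpoint.

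Three stronger readings are tempting, and the documents do not support them.
- A reader might infer that the protocol synopsis already requires a seronegative mITT: "The difference in CHIKV SNA seroresponse rates (PXVX0317 minus placebo) among baseline seronegative participants will be calculated". That sentence fits the IEP, which is seronegative by definition. The synopsis defines the mITT without a serostatus condition, and Protocol 9.6.2.1.1 adds none to the mITT repeat.
- A reader might infer that seropositives below 10% are hidden. SAP 8.2.1 counts them by arm in the mITT. Only outcomes by serostatus are missing.
- A reader might infer that the mITT could fail the clinical-relevance criterion. That criterion applies to the IEP, and its value is redacted.

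**Conclusion.** The point holds as a minor one about supportive analyses. The mITT repeat and both imputation analyses mix prior antibody with the problems that they are meant to probe, and no planned mITT outcome separates it. The primary IEP analysis, its error control and superiority over placebo are unaffected.

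On the stated assumptions the loss in the mITT seroresponse difference is at most 0.9 to 1.7 points at 1% to 2% seropositive, 4.3 at 5% and 7.7 at 9%. The lower bound falls by slightly more. The true figure depends on a seropositive rate that the documents do not give, and is smaller if some seropositives lie below the threshold.

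Under most of the assumed titers, a Day 1 covariate cuts the mITT GMT standard error by roughly 3–7% at 2%, 6–13% at 5% and 9–17% at 9% seropositive. The gain is less if vaccinated seropositives respond poorly. The covariate improves precision but does not remove the dilution; the seronegative restriction does that.

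**What to change.** 1. In SAP 6.5.3 and 8.4, add a baseline-seronegative mITT row for the Day 22 seroresponse difference and GMT, including the nonresponder and LOCF versions. Place it next to the planned all-comer mITT row, which stays.
2. In SAP 6.1.2 and 6.6, add log10 Day 1 titer (LLOQ/2 if below the LLOQ) as a covariate in the mITT GMT model. The IEP model needs no change, because baseline is constant there.
3. In Appendix I, move the baseline-serostatus outcome tables (14.2.1.1.5 and 14.2.2.1.5) from the IEP to the mITT.

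The cost is SAP wording, one model term and some extra table rows; the Day 1 samples are already collected. Participants without a Day 1 titer drop out of the adjusted model and the seronegative row, but remain in the all-comer seroresponse row. Their number should be reported.

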9.2 Analysis Populations

Analysis will be based on the following study populations:

Enrolled Population: All screened participants who sign an ICF, are entered in the EDC database, and meet all eligibility criteria.

Randomized Population: All screened participants who provide informed consent and provide demographic and other screening measurements and are randomized in the EDC.

Exposed Population: All participants in the randomized population who receive IP.

Safety Population: All participants in the exposed population who provide safety assessment data. Safety endpoints will utilize the safety population, analyzed as treated.

Modified Intent-to-Treat population: All randomized participants who are vaccinated and have at least one postinjection anti-CHIKV SNA titer result, analyzed as randomized.

Immunogenicity Evaluable Population: All participants in the mITT population who: i) provide evaluable serum sample results for the Day 22 time point within the required time frame of Day 19 through Day 27, inclusive, ii) have no measurable anti-CHIKV SNA at Day 1, iii) have no important protocol deviation or other reason to be excluded as defined prior to unblinding. The IEP is the primary population for all immunogenicity analyses.

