## 5.3 Analysis Populations

Analyses are based on the following study populations:

**Randomized Population:** All screened participants who provide informed consent and provide demographic and other screening measurements and are randomized (i.e., have a randomization number assigned within the EDC system). Most baseline summaries and the IP administration summary use the randomized population.

**Exposed Population:** All participants in the randomized population who receive IP.

**Safety Population:** All participants in the exposed population who provide safety assessment data. This generally includes any participant who was not lost to follow-up at Day 1 (baseline), as they are at risk for reporting an SAE. Participants are analyzed as treated (i.e., according to the treatment a participant received, rather than the treatment to which the participant was randomized). All safety analyses use the safety population.

**Modified Intent-to-Treat (mITT) Population:** All randomized participants who are vaccinated and have at least one post-injection anti-CHIKV human SNA assay result. Participants are counted in the group to which they were randomized. Primary and secondary immunogenicity analyses are repeated for the mITT population as a measure of robustness of the results.

**Immunogenicity Evaluable Population (IEP):** The IEP includes all participants in the mITT population who:

- Provide evaluable serum sample results for the relevant post-vaccination time points, and within the required time frames:
  - Day 22: Day 19 through Day 27, inclusive.
- Have no measurable ( $\geq$ LLOQ) anti-CHIKV human SNA assay titer at Day 1 (baseline), i.e., seronegative at baseline. Note that participants with missing Day 1 (baseline) are excluded from IEP.
- Have no important protocol deviation deemed exclusionary or other reason to be excluded as defined prior to unblinding.

The IEP is the primary population for all immunogenicity analyses.

**CHIKV Genotype Subset:** The CHIKV genotype subset includes those IEP participants who received PXVX0317 and are selected for genotype analysis. See Section 8.4.3 for details.

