## APPENDIX I LIST OF TABLES, FIGURES, AND LISTINGS

Note the list of TFLs is a living document and subject to changes during the study.

Table	Title
Baseline	
14.1.1	Participant Enrollment by Site – Randomized Population
14.1.2	Analysis Populations – All Participants
14.1.3	Participant Disposition – Randomized Population
14.1.4.1	Demography – Randomized Population, Both Ages Pooled and by Age Group
14.1.4.2	Demography – Safety Population, Both Ages Pooled and by Age Group
14.1.4.3	Demography – Modified Intent-to-treat Population, Both Ages Pooled and by Age Group
14.1.4.4	Demography – Immunogenicity Evaluable Population, Both Ages Pooled and by Age Group
14.1.5	Medical History – Randomized Population
14.1.6	Timing of Blood Sample Collection – Randomized Population
14.1.7.1	Important Protocol Deviations – Randomized Population
14.1.7.2	Reasons for Exclusion from Analysis Populations – Randomized Population
14.1.8.1	Prior and Concomitant Medications by Descending Frequency within ATC Class and Drug Name – Safety Population
14.1.8.2	Concomitant Vaccines by Descending Frequency within ATC Class and Drug Name – Safety Population
Immunogenicity	
14.2.1.1.1	Anti-CHIKV SNA Seroresponse Rate by Treatment Group and Visit – Immunogenicity Evaluable Population, Both Ages Pooled and by Age Group
14.2.1.1.2	Anti-CHIKV SNA Seroresponse Rate by Treatment Group and Visit – Immunogenicity Evaluable Population, Both Ages Pooled by Sex Subgroups
14.2.1.1.3	Anti-CHIKV SNA Seroresponse Rate by Treatment Group and Visit – Immunogenicity Evaluable Population, Both Ages Pooled by Race Subgroups
14.2.1.1.4	Anti-CHIKV SNA Seroresponse Rate by Treatment Group and Visit – Immunogenicity Evaluable Population, Both Ages Pooled by Ethnicity Subgroups
14.2.1.1.5	Anti-CHIKV SNA Seroresponse Rate by Treatment Group and Visit – Immunogenicity Evaluable Population, Both Ages Pooled by Baseline Serostatus Subgroups
	Note: Only needed if baseline seropositive rate is <math>\geq 10\%</math>.
14.2.1.2.1	Anti-CHIKV SNA Seroresponse Rate by Treatment Group and Visit – mITT Population, Both Ages Pooled and by Age Group
14.2.1.2.2	Anti-CHIKV SNA Seroresponse Rate by Treatment Group and Visit, Sensitivity Analyses – mITT Population, Both Ages Pooled and by Age Group
14.2.2.1.1	Anti-CHIKV SNA GMT by Treatment Group and Visit – Immunogenicity Evaluable Population, Both Ages Pooled and by Age Group

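### The Day 22 nonresponder sensitivity analysis is confined to the mITT, so vaccinated participants with no post-dose titer are dropped rather than counted as nonresponders

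*SAP*

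**What the plan says.** SAP 6.5.3 sets out two sensitivity analyses for the coprimary endpoints, the Day 22 seroresponse difference and the Day 22 GMTs. In the nonresponder analysis, a missing Day 22 "titer value is imputed as the assay LLOQ/2, even for participants in the PXVX0317-vaccinated group". In the LOCF analysis, "Participants' Day 15 immunogenicity value is substituted for the missing Day 22 anti-CHIKV SNA titer value". Both are to be "reported for the mITT population to assess the robustness of primary endpoint results to informative missingness", and SAP 8.4 repeats this purpose and population. The table list in SAP Appendix I carries the sensitivity outputs only as "Sensitivity Analyses – mITT Population, Both Ages Pooled and by Age Group".

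SAP 5.3 defines the mITT as "All randomized participants who are vaccinated and have at least one post-injection anti-CHIKV human SNA assay result". Protocol 9.2 has the same condition: participants must "have at least one postinjection anti-CHIKV SNA titer result, analyzed as randomized". SAP 5.3 also defines a wider set, the Exposed population: "All participants in the randomized population who receive IP". Neither document plans an imputed analysis in that set or in the Randomized population.

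**The concern.** Entry to the mITT depends on whether a post-dose outcome was observed. An analysis meant to test sensitivity to missing outcomes is thus run in a set from which participants with no outcome at all have already been removed. For them the rule that a missing result counts as a failure never operates.

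The primary analysis does not impute missing titers (Protocol 9.5), and LOCF needs a Day 15 value, so neither reaches these participants. The first coprimary criterion requires the lower confidence limit of the seroresponse difference to clear a margin, not merely to exclude zero. A lower limit that leaves out some vaccinated participants is therefore a weaker check on that criterion than the SAP's stated purpose suggests.

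**Working it through.** **Who is reached by the imputation.** Setting SAP 5.3 beside SAP 6.5.3, for vaccinated participants:

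- Day 22 titer present: observed value used.
- Day 22 titer missing, another post-injection titer present: in the mITT, imputed as LLOQ/2.
- No post-injection titer at all: not in the mITT, not imputed, absent from the denominator.

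**The plan's own figures.** Protocol 9.1 and SAP 4.1 assume 10% nonevaluable: 200 × (1 − 0.10) = 180 per arm, as stated. The expected vaccine rate is redacted. Against 5% on placebo, two-sided alpha 0.05, 180 per arm gives power of 99.2% at a vaccine rate of 20%, 99.98% at 25%, and effectively 100% from 30% upward. The stated power above 99.9% therefore reproduces for any vaccine rate of 25% or more. The stated half-width of ±5.4% reproduces with the Wald formula at an assumed 90%: 1.96 × √(0.90×0.10/180 + 0.05×0.95/180) = 5.42%. The stated ±6.9% reproduces at an assumed 77% (6.92%). These rates are back-solved, not taken from the documents.

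**Size of the gap.** Inputs: 200 vaccinated per arm (SAP 2.2 gives 200 planned per group; all are assumed dosed), placebo rate 5% (Protocol 9.1), Newcombe hybrid score interval (SAP 6.1.1). Assumptions: vaccine rate 80% or 90%; m participants per arm with no post-injection titer; everyone else has a Day 22 result.

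The Newcombe lower limit is

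L = d − √[(p₁ − l₁)² + (u₂ − p₂)²],

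where d = p₁ − p₂, l₁ is the Wilson lower limit for vaccine and u₂ the Wilson upper limit for placebo. In the mITT the denominator is 200 − m. In the Exposed population it is 200 with the same responders, so d is multiplied by (200 − m)/200. Expected counts are used, so they need not be whole numbers.

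Worked case, 90% versus 5%, m = 10:

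- mITT: 171/190 = 90.0% and 9.5/190 = 5.0%; d = 85.0%; l₁ = 84.91%, u₂ = 9.09%. L = 0.850 − √(0.0509² + 0.0409²) = 78.5%.
- Exposed: 171/200 = 85.5% and 9.5/200 = 4.75%; d = 80.75%; l₁ = 79.95%, u₂ = 8.64%. L = 0.8075 − √(0.0555² + 0.0389²) = 74.0%.

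| Vaccine rate (assumed) | m per arm | L in mITT | L in Exposed | Fall (points) |
|---|---|---|---|---|
| 80% | 2 | 67.70% | 66.94% | 0.8 |
| 80% | 5 | 67.64% | 65.75% | 1.9 |
| 80% | 10 | 67.53% | 63.78% | 3.7 to 3.8 |
| 90% | 2 | 78.63% | 77.72% | 0.9 |
| 90% | 5 | 78.57% | 76.30% | 2.3 |
| 90% | 10 | 78.47% | 73.97% | 4.5 |

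In these cases the planned mITT nonresponder analysis would show none of the fall. No size is given for the GMT endpoint, because the documents state neither the LLOQ nor a variance for the log titers.

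**The case against.** Four points can fairly be made on the other side.

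First, the gap is smaller than early dropout as a whole. Under Protocol 6.7 an early discontinuation visit follows the Visit 3, 4 or 7 schedule, each of which includes an SNA draw, and Protocol 3.2.6.1 and 7.1 confirm sampling at early discontinuation. A leaver who attends can enter the mITT and be imputed as a failure. This stands, and it narrows the gap. It does not close it: Protocol 3.9 asks only that efforts be made to hold the visit, and Protocol 4.3.3 makes it subject to the participant's agreement.

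Second, a reader might take the 10% nonevaluable allowance as the number with no titer. At 20 per arm and 90% versus 5%, the lower bound would fall from 78.3% to 69.4%. The documents do not support that reading. Participants with an out-of-window Day 22 sample, baseline seropositivity or an exclusionary deviation also leave the IEP, yet SAP 6.5.3 places them in the mITT. Twenty per arm is an extreme upper case.

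Third, a reader might infer that the excluded participants are the ones most likely to be informatively missing. Nothing in the documents shows this. The trial is single-dose and double-blind, and no mechanism is given that links the absence of every sample to the unseen titer. The point does not need that inference; it rests only on the mismatch between the stated purpose and the population.

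Fourth, the analysis carries no success criterion, and SAP 8.1 already summarizes reasons for exclusion from each population by arm. A reader who can identify those with no titer could rebuild the seroresponse figure by hand. That helps, but it is not a planned result and would not give the GMT analysis, which needs a model fit.

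**Conclusion.** The point holds in a limited form. As written, the nonresponder analysis omits vaccinated participants with no post-dose titer, and no other planned analysis or listed table includes them as failures. It does count as failures those with another post-dose titer but no Day 22 value.

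The lower bound moves by about 1 point for 2 such participants per arm, about 2 points for 5, and about 4 to 4.5 points for 10. This rests on assumed vaccine rates of 80% to 90%, 5% on placebo, 200 vaccinated per arm and equal numbers without a titer in each arm. The actual number is not given and is probably well below 20 per arm.

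It would be wrong to conclude that the coprimary result is in danger. Power for superiority stays near 100% even when 20 per arm are counted as failures. Whether the lower-bound criterion could be affected cannot be judged, because the margin is redacted; it would matter only if the observed bound lay within a few points of it.

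**What to change.** In SAP 6.5.3 and 8.4, add a nonresponder analysis of the Day 22 coprimary endpoints in the Exposed population (all randomized and vaccinated participants), analyzed as randomized. Every missing Day 22 result is set to LLOQ/2 and counted as a nonresponder, including for participants with no post-dose sample. Keep the mITT row beside it, and report by arm the number of vaccinated participants with no post-injection titer. Add the row to Tables 14.2.1.2.2 and 14.2.2.2.2 and amend their titles, which now name the mITT alone. The LOCF analysis can stay in the mITT, since it needs a Day 15 value.

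The cost is one extra row in each table and a supportive estimate that may look slightly less favourable. No new data are needed, no alpha is spent and the primary analysis is unchanged.
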